1.2. Schema

The set-up of each of the 3 Parts of this study are summarized in Figure 1 (Part 1), [Figure 2](#) (Part 2) and [Figure 3](#) (Part 3).

Figure 1. Overall Study Design - Part 1

[figure not shown]

Figure 2. Overall Study Design - Part 2

[figure not shown]
[figure not shown]

Figure 3. Overall Study Design - Part 3 [if conducted]

1.3. Schedule of Activities

The **SoA tables** provide an overview of the protocol visits and procedures; refer to **Section 8** of the protocol for detailed information on each procedure and assessment required for compliance with the protocol. The investigator may schedule visits (unplanned visits) in addition to those listed here, in order to conduct evaluations or assessments required to protect the well-being of the participant.

SoA - TABLE A. Part 1 – Single, Escalating Doses of PF-07202954/Placebo (Cohorts 1 and 2)[refer to sub-sections in [Section 8](#) for additional details]

Visit Identifier (for list of abbreviations refer to Section 10.8)	Screen (≥ 28 days)	Periods 1-4 [dosing separated by ≥ 10 days between Periods]												Follow-up		D/C	
		-1			1			2			3			8±2 days ^a	30±2 days ^a		
		N/A	0	0.5	1	2	3	4	5	8	12	16	24	36	48	72	
Informed consent & demography	x																
Outpatient visit	x															x	
Inpatient stay at CRU		x	→	→	→	→	→	→	→	→	→	→	→	→	x		
Assessment of eligibility (& update on Day -1 in Period 1, only)	x	x															
Medical history (with update on Day -1 in Period 1, only)	x	x															
PE (plus height & body weight at Screen, only) ^b	x	x															
Review alcohol/tobacco use & contraception use	x	x													x	x	x ^c
Review prior or concomitant (non-) drug treatments	x	x													x	x	x
Supine 12-lead ECG ^d	x ^d		x	x	x	x	x	x	x	x	x	x	x	x	x ^d		x ^d
Single , supine vital signs (includes BP and pulse rate at all times)	x		x	x	x	x	x	x	x	x	x	x	x	x	x	x	x
SAE and AE monitoring	x	x	→	→	→	→	→	→	→	→	→	→	→	→	→	x	x
Continuous cardiac telemetry monitoring		x ^e	x	→	→	→	→	→	→	x							
Standard meals ^f		x	x					x	x	x	x	x	x	x	x	x	
Blinded study intervention administration			x ^g														
Blood Sampling [refer to Section 8.5 and Section 10.2] for –																	
Clinical laboratory tests (after ≥ 10 hour fast)	x	x ^h											x		x	x	x
Serum FSH [in females amenorrhoeic ≥ 12 months, only]	x																
Serum pregnancy testing [in all females]	x	x ^h												x		x	
CC1 [REDACTED]													x		x		
Pre-specified PGx and Banked Prep D1.5 (Period 1 only)			x														
Plasma PK [timepoints may be revised prior to dosing, if needed]		x	x	x	x	x	x	x	x	x	x	x	x	x	x	x	x
CC1 [REDACTED]													x		x	x	
Urine [refer to Section 10.2] for –																	
Spot sample for drug test	x	x ^h															
Spot sample for urinalysis, UACR, UPCR (+microscopy, if needed)	x	x ^h											x		x	x	x
CC1 [REDACTED]													x				

a. Onsite Follow-up visit (8±2 days) and Follow-up telephone contact (30±2 days) to occur relative to last dose of investigational product in Period 4.

b. Complete PE at Screen *or* upon admission in Period 1; otherwise, brief PE for findings at previous PE or new/open AEs **only**, at investigator discretion.c. Confirmation of appropriate contraception use, **only**.d. **Single** ECG at screen, on-site Follow-up visit, and D/C; **triplicate** supine 12-lead ECGs at all other timepoints.e. Baseline telemetry must be captured for ≥ 2 hours while participant is awake between admission on Day -1 and 0H on Day 1 of Period 1, **only**.f. **Standard** meals served at approximate clock times matching nominal time 0H, and at 5H, and 12H relative to dosing on Day 1, while inpatient.g. Following ≥ 10 hour overnight fast, dosing at approximately 8:00AM (± 2 H) to occur **with** standard morning meal provided ~30 mins prior to dosing at 0H.h. Results must be reviewed prior to dosing on Day 1 in **each** Period.

PFIZER CONFIDENTIAL

SoA - TABLE B. Part 2 – Repeated, Escalating Doses of PF-07202954/Placebo (Cohorts 3, 4, 5, 6, 7, and optional Cohort 8)

[refer to sub-sections in Section 8 for additional details]

Protocol Activity (for list of abbreviations refer to Section 10.8)	Screen		Baseline		All at 0H (prior to dosing) unless otherwise specified												Off-Drug			Follow-up			D/C	
	-≤28	-≤2 ^a	-2	-1	1	2	3	4	5	6	7	8	9	10	11	12	13	14	15	16	17	22±2 ^b	44±2 ^b	
Study Day	-≤28	-≤2 ^a	-2	-1	1	2	3	4	5	6	7	8	9	10	11	12	13	14	15	16	17	22±2 ^b	44±2 ^b	
Informed consent & demography	x																							
Outpatient visit	x	x																				x		
Inpatient stay at CRU					x																	x		
Medical history (update)	x		x																			x		
Review alcohol/tobacco use & contraception use	x		x																		x	x		x
Review prior or concomitant (non-) drug treatments	x		x																		x			
PE (includes height at Screen) ^c	x		x																					
Body weight	x						x														x	x		
FibroScan® (after ≥4 hour fast)	x	x ^{a,j}																						
CCI																								
SAE and AE monitoring	x	x	x																		x	x	x	x
Supine 12-lead ECG ^d	x ^d																				x ^d	x ^d	x ^d	x ^d
Single , supine vital signs (BP and pulse rate)	x																				x	x		x
Standardized meals ^f				x																	x	x	x	
Blinded study intervention administration ^g																								
Blood sampling [refer to Section 8.5 and Section 10.2] for:																								
Clinical laboratory tests	x ^h	x ^{a,j}																			x ^h	x ^h	x ^h	x
Serum FSH [females amenorrhoeic ≥12-months, only]	x																							
Serum pregnancy testing (in all females)	x	x ^j																						
Plasma PK ⁱ																				x ⁱ	x ⁱ	x ⁱ	x	
CCI																								
Urine sampling [refer to Section 10.2] for:																								
Urine drug test	x	x ^j																						
Urinalysis including microscopy, UACR, UPCR	x	x																		x	x	x	x	

a. Separate from 1st Screen visit; can be conducted post ≥4 hour fast on Day -2 with **double-confirmation** on FibroScan® + LFTs **before** Day -2 **CCI**.

b. Onsite Follow-up visit (8±2 days; ie, Day 22±2) and Follow-up telephone contact (30±2 days; ie, Day 44±2) to occur relative to last dose of investigational product.

c. Complete PE at Screen **or** upon admission on Day -2; otherwise, brief PE for findings at previous PE or new/open AEs **only**, at investigator discretion.d. **Single** 12-lead ECG at screen, discharge, on-site Follow-up visit, and D/C; **triplicate** 12-lead ECGs at 2H (approximately T_{max}) post dose on Days 4 and 10.e. Includes assessment at 0H **plus** an additional assessment at approximately 2H (approximately T_{max}) post dose.f. **Standard** meals served at approximate clock times matching nominal time 0H, and at 5H, and 12H relative to dosing at 0H, each day while inpatient.g. Following ≥10 hour overnight fast, dosing at approximately 8:00AM (±2H) to occur **with** standard morning meal provided ~30 mins prior to dosing at 0H.

h. Collection following ≥10 hour overnight fast.

i. PK samples collected prior to dose; **in addition**, on Day 15 [24H (**SoA - Table C**), 36H], Day 16 [48H], and Day 17 [72H] relative to dosing at 0H on Day 14.j. Results for these collections must be reviewed, by investigator **before** Day -2 **CCI**.

SoA - TABLE C. Part 2 – Repeated, Escalating Doses of PF-07202954/Placebo (Cohorts 3, 4, 5, 6, 7, and optional Cohort 8) – Days -1, 1, 7, 14 only
 [refer to sub-sections in [Section 8](#) for additional details]

Hours Relative to Dosing at 0H ^a (for list of abbreviations refer to Section 10.8)	0	0.5	1	2	3	4	5	8	10	12	14	16	24 ^b
Continued inpatient stay at CRU	→	→	→	→	→	→	→	→	→	→	→	→	→
SAE and AE monitoring	→	→	→	→	→	→	→	→	→	→	→	→	→
Body weight (Days 1, 7, 14)	x												
Triplet , supine 12-lead ECG (Days 1, 7, 14)	x		x	x		x		x		x			x
Single , supine vital signs (includes BP and pulse rate) - Days 1, 7, 14	x		x	x		x		x		x			x
Standard meals ^c	x						x			x			x
Blinded study intervention administration – Days 1, 7, 14 ^d	x												
Blood sampling [refer to Section 8.5 , Section 8.8 , and Section 10.2] for –													
Clinical laboratory tests after ≥10 hour fast – Days 1, 7, 14	x												
Pre-specified PGx and Banked Prep D1.5 – for DNA (Day 1, only)	x												
Serum extracellular vesicles (Days 1, 14)	x												
Plasma PK – timepoints may be revised prior to dosing, if needed – Days 1, 7, 14	x	x	x	x	x	x	x	x	x	x	x	x	x
CCI													
Urine sampling [refer to Section 8.5 , Section 8.8 , and Section 10.2] for –													
Spot collection for urinalysis including microscopy, UACR, UPCR – Days 1, 7, 14	x												
Pre-dose spot urine for PK - Urine blank on Day 1	x												
24-hour interval for PF-07202954 PK (Day 14)	x	→	→	→	→	→	→	→	→	→	→	→	x
CCI													

a. On Day -1, nominal time to approximately match clock time of collection planned on Day 1 to permit time-matched comparison.

b. Equates to D2,0H (on Day 1), D8,0H (on Day 7), and D15,0H (on Day 14) – refer to [Table B](#) for other procedures on these days.

c. **Standard** meal served ~30 mins prior to dosing at 0H *plus* at 5H, and 12H relative to approximate clock times matching dosing on Day 1.

d. Following ≥10 hour overnight fast, dosing at approximately 8:00AM (±2H) to occur *with* standard morning meal.

e. **CCI**

SoA - TABLE D. Part 3 (if Conducted) – Food Effect (Periods 1 & 2, inclusive) – [refer to sub-sections in Section 8 of additional details]

Visit Identifier [for abbreviations refer to Section 10.8]	Screen (≤ 28 days)	Periods 1 and 2 [dosing separated by ≥ 5 days between Periods] Procedures at 0H (prior to dosing) unless otherwise specified												Follow-up		D/C
		-1	1					2		3		4		8±2 days ^a	30±2 days ^a	
Day Identifier	N/A	0	0.5	1	2	3	4	5	8	12	16	24	36	48	72	
Hours Post Dose																
Informed consent & demography	x															
Outpatient visit	x														x	
Inpatient stay at CRU		x	→	→	→	→	→	→	→	→	→	→	→	x		
Assessment of eligibility	x	x ^b														
Medical history	x	x ^b														
PE (including height & body weight at Screen, only) ^c	x	x ^b												x	x	
Review alcohol/tobacco use & contraception use	x	x ^b												x ^b	x	x ^d
Review prior or concomitant (non-) drug treatments	x	x ^b												x	x	x
Single , supine 12-lead ECG	x		x			x ^e								x	x	x
Single , supine vital signs (includes BP and pulse rate)	x		x			x ^e								x	x	x
SAE and AE monitoring	x	x	→	→	→	→	→	→	→	→	→	→	→	→	→	x
Standard meals ^f		x						x	x	x	x	x	x	x	x	
High-fat/high-caloric meal			x ^g													
Open-label study intervention administration			x ^g													
Blood Sampling [refer to Section 8.5 and Section 10.2] for –																
Clinical laboratory tests [after ≥ 4 hour fast]	x	x ^h										x		x	x	x
Serum FSH [in females amenorrhoeic ≥ 12 -months, only]	x															
Serum pregnancy testing (in all females)	x	x ^h											x ^b	x		x
Pre-specified PGx and Banked Prep D1.5 (Period 1 only)			x													
Plasma PK [nominal times may be revised prior to P1D1]			x	x	x	x	x	x	x	x	x	x	x	x	x	x
Urine Sampling [refer to Section 10.2] for –																
Urine drug test	x	x ^{b,h}														
Urinalysis, UACR, UPCR (and microscopy, if needed)	x	x ^h									x		x	x	x	x

a. On-site Follow-up visit (8 ± 2 days) and Follow-up telephone contact (30 ± 2 days) to occur relative to last dose of study intervention in Period 2.

b. Procedures to be completed upon admission in Period 1; *plus*, upon discharge in Period 2, *when denoted*.

c. Complete PE at either Screen *or* upon admission in Period 1; otherwise, brief PE for findings at previous PE or new/open AEs *only*, at investigator discretion.

d. Confirmation of appropriate contraception use, *only*.

e. Collection to occur at T_{max} post dose, as observed in Part 1.

f. Meals served at approximate clock times matching nominal time 0H (on non-dosing days while inpatient), 5H, and 12H relative to dosing on Day 1.

g. Dosing at 8:00AM (± 2 H) in both Periods; as dictated by randomization scheme, dosing to occur with either high-fat/high-caloric meal (ie, provided ~ 30 mins prior to dosing at 0H and expected to be completed ~ 10 mins prior to dosing) *or* with water following an overnight fast of ≥ 10 hours.

h. Results must be reviewed, by investigator, prior to dosing on Day 1.

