2.2.3. Biopharmaceutics

PF-07202954 is a weak base with pKa values of 7.5 and 2.5, thus exhibiting a strong pH-dependent change in solubility. It has high thermodynamic aqueous solubility at physiological pH. The solubility of PF-07202954 in simulated gastric fluid (pH 2.7) and unbuffered water (pH 8) is >27 mg/mL and 0.13 mg/mL, respectively. Solubility in simulated fasted and fed state intestinal fluids (pH 6.9 under both conditions) was observed to be 0.7 mg/mL and 1.2 mg/mL, respectively. Solubility of PF-07202954 is high relative to

the predicted clinical FIH dose range, thus the risk for solubility/dissolution-limited absorption and exposure-limiting precipitation is perceived to be low. Food is expected to have minimal impact on PF-07202954 PK – refer to [Section 4.2.5](#). Preliminary in vitro studies suggest PF-07202954 exhibits moderate in vitro permeability and is a substrate for the intestinal efflux transporters (P-gp and BCRP) that could potentially lead to non-linear plasma PK and high variability in exposure at lower doses.

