For a given participant, dosing will be separated by **≥10 days**, with this planned dosing interval deemed sufficient based on the predicted PF-07202954 effective half-life of approximately 8 hours. In addition, this interval accounts for the required time for review of the safety, tolerability, and PK data from each dosing period before making a decision on the subsequent PF-07202954 dose to be evaluated. The planned doses in the escalation sequence (refer to [Table 3](#)) may be modified or repeated, as guided by emerging safety and PK data but will follow the dose-escalation rules defined in [Section 6.6.1](#). The data from participants as they receive placebo will be pooled and compared to data from each active dose to determine the next escalating dose of PF-07202954. The assessment of the full range of doses will require the planned 8 Periods of dosing (4 Periods per participant). In the event that additional dose-escalation is no longer warranted (eg, maximum tolerated dose identified, clear evidence of plateau in plasma PK based on observed data with at least 2 dose-levels), the additional periods in this 4-Period, cross-over design may be used to repeat a previously administered dose, study a lower and/or intermediate dose, and/or undertake an exploratory assessment of plasma PK with dosing following an overnight fast of **≥10 hours** *or* dosing following a high fat/high caloric morning meal (compared to dosing following a standard morning meal in previous Periods within the same cohort) to explore any potential food effect. And pending observed plasma PK data from Part 1, this study may also conduct Part 3 – refer to [Section 4.2.4](#) – to compare plasma PK following dosing in the fasted state (Reference) to dosing with a high-fat/high-caloric morning meal (Test).

4.2.3. Rationale for Part 2

[figure not shown]

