4.3.2. Human Exposure Limits

Guided by the target organs of toxicity identified in the completed GLP, 6 week studies in rats and monkeys (refer to [Section 2.2.4](#), [Table 3](#) and [Table 4](#)), the PK exposure limits in this study are proposed as –

- **In Part 1 and Part 2: Total C_{max} : 1450 ng/mL** – reflecting the *conservative* 1/10th of the exposure at the NOAEL dose (100 mg/kg/day) in the 6 week toxicity study in monkeys [for the convulsions observed in 1 monkey in the exploratory toxicity study following PF-07202954 dose of 500 mg/kg/day];
- **In Part 1: Total AUC_{24} : 18,400 ng•h/mL** – reflecting 50% of exposure in males at the NOAEL dose (300 mg/kg/day) in the 6-week toxicity study in rats [for adverse renal findings];
- **In Part 2: Total AUC_{24} : 3,680 ng•h/mL** – reflecting 10% of exposure in males at the NOAEL dose (300 mg/kg/day) in the 6-week toxicity study in rats [for adverse renal findings] with revision to this stopping limit to be considered, via a protocol amendment post formal interim analysis, based on observed data in Part 1 *and* Part 2 in this study.

4.3.3. Rationale for Dose Selection in Part 1

The objective of Part 1 of this study is to explore the safety, tolerability, and plasma PK of PF-07202954 after administration of single escalating oral doses across a wide exposure range and potentially up to the maximum predefined human exposure limits ([Table 3](#)). Dosing will occur with a *standard* morning meal. The doses presented are projected based on nonclinical data and may be modified based on emerging human safety, tolerability, and PK data. Human PK parameter estimates, toxicokinetic data, and projected effective concentrations were used to establish the initial range of planned doses in this study. The projected human exposures are based on assuming dose-proportional increases in exposure within the planned dose range.

Table 3. Predicted Human Exposures at Proposed Single Doses of PF-07202954

Dose (mg)	Total Concentrations		Safety Margins ^{b,c}	
	C _{max} ^a (ng/mL)	AUC ₂₄ ^a (ng·h/mL)	C _{max} ^b	AUC ₂₄ ^c
10	10	180	140	102
30	31	540	46	34
100	100	1800	14	10
300	310	5400	4.6	3.4
600	620	11,000	2.3	1.7
1000 ^d	1040	18,000	1.4	1.0 ^d

- a. C_{max} and AUC₂₄ were estimated using projected human PK parameters for PF-07202954 using CL_{plasma}=3.34 mL/min/kg; V_{ss}=2.3 L/kg; F=0.32; ka=0.2 h⁻¹; human fu=0.382; body weight=70 kg.

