7.1.1. ECG Changes

A participant who meets either of the bulleted criteria below based on the average of triplicate ECG readings will be withdrawn from the study intervention.

- QTcF >500 msec.
- Change from baseline: QTcF >60 msec.

If a clinically significant finding is identified (including, but not limited to, changes from baseline in QTcF after enrollment), the investigator or qualified designee will determine if the participant can continue in the study and if any change in participant management is needed. This review of the ECG printed at the time of collection must be documented. Any new clinically relevant finding should be reported as an AE.

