**TABLE 7. PLASMA PK PARAMETERS TO BE SUMMARIZED DESCRIPTIVELY**

Parameter	Summary Statistics
AUC inf , AUC last , C max , AUC inf(dn) , AUC last(dn) , AUC tau , AUC tau(dn) , C max(dn) , CL/F, V z /F, C min , PTR, AUC tau , C av , R ac,AUCtau , and R ac,Cmax	N, arithmetic mean, median, %CV, standard deviation (SD), minimum (min), maximum (max), geometric mean and geometric %CV
T max , T lag	N, median, min, max.
t 1/2	N, arithmetic mean, median, %CV, SD, min, max.

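### Part 2 sets its Day 4 and Day 10 triplicate ECGs at 2 h and calls that approximately Tmax, while the protocol's own projection parameters put Tmax near 6.3 h (minor)

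*Protocol*

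**What the plan says.** Protocol Section 1.3, SoA Table B, footnote d places triplicate "12-lead ECGs at 2H (approximately T_{max}) post dose on Days 4 and 10". No source for a 2 h Tmax is given. Footnote e uses the same label, but I cannot read with certainty which row it belongs to, so this point rests on footnote d alone.

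Footnote a of Table 3 (Section 4.3.3), repeated under Table 4 (Section 4.3.4), gives the projection inputs: plasma clearance 3.34 mL/min/kg, Vss 2.3 L/kg and "F=0.32; ka=0.2 h⁻¹; human fu=0.382; body weight=70 kg". Section 4.2.2 adds a predicted "PF-07202954 effective half-life of approximately 8 hours".

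Three other provisions bear on the timing:

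- SoA Table C schedules serial triplicates, "supine 12-lead ECG (Days 1, 7, 14" being the row label. As the columns read, the times are 0, 1, 2, 4, 8, 12 and 24 h.
- SoA Table D, footnote e, times the post-dose ECG in Part 3 differently: "Collection to occur at T_{max} post dose, as observed in Part 1".
- Section 4.2.3 starts Part 2 only after safety and PK from at least three Part 1 dose levels have been reviewed.

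**The concern.** The label presents the Day 4 and Day 10 ECGs as peak checks between the serial ECG days. An absorption rate constant of 0.2 per h with an 8 h half-life describes slow absorption, and a peak at 2 h does not follow from it.

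Delayed repolarization is a named nonclinical risk in Table 1. Under Section 7.1.1, a participant who crosses a QTcF threshold "based on the average of triplicate ECG readings will be withdrawn from the study intervention". If the projection is right, the two added ECGs are taken while concentration is still rising. The Day 4 check would then sample no higher exposure than the Day 1 ECGs already did, although accumulation is essentially complete by Day 4.

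**Working it through.** **Inputs** (footnote a of Tables 3 and 4): CL 3.34 mL/min/kg, Vss 2.3 L/kg, F 0.32, ka 0.2 per h, 70 kg. **Assumption (mine):** one compartment with Vss as its volume, first-order absorption, and doses every 24 h superposed.

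- CL = 3.34 × 60 / 1000 × 70 = 14.03 L/h
- V = 2.3 × 70 = 161 L
- ke = 14.03 / 161 = 0.0871 per h, so half-life = ln 2 / 0.0871 = 7.96 h (protocol: about 8 h)

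**Reproducing the protocol's figures** (ng/mL and ng·h/mL):

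| Case | Model Cmax | Protocol Cmax | Model AUC24 | Protocol AUC24 |
|---|---|---|---|---|
| 1000 mg, single dose (Table 3) | 1,047 | 1,040 | 17,963 | 18,000 |
| 100 mg, steady state (Table 4) | 131 | 130 | 2,281 | 2,300 |
| 160 mg, steady state (Table 4) | 210 | 210 | 3,650 | 3,600 |
| 80 mg, steady state (Section 4.3.1) | 105 | 106 | 1,825 | 1,840 |

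**Tmax from the same model**

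- Single dose: ln(ka/ke) / (ka − ke) = ln(0.2/0.0871) / 0.1129 = 7.36 h
- Steady state: ln{ka(1 − e^(−24ke)) / [ke(1 − e^(−24ka))]} / (ka − ke) = 6.27 h. Superposition gives 6.27 h on Day 4 and on Day 10.

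**Where the ECGs fall** (160 mg; Cmax is 167.4 on Day 1 and 210.1 on Day 4):

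| ECG | Share of that day's Cmax | Share of Day 1 Cmax |
|---|---|---|
| Day 1, 8 h | 99.7% | 0.997 |
| Day 4, 2 h | 159.1/210.1 = 76% | 159.1/167.4 = 0.950 |
| Day 7, 4 h | 94% | 1.185 |
| Day 7, 8 h | 98% | 1.227 |

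Day 10 at 2 h is also at 76% of that day's Cmax. The Day 4 peak is 210.1/167.4 = 1.255 times the Day 1 peak.

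**Sensitivity on Day 4**

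- ka of 0.1, 0.15 and 0.3 per h: Tmax is 7.9, 7.0 and 5.2 h, and the 2 h sample is at 78%, 76% and 79% of Cmax.
- Half-life of 5 and 12 h (ka 0.2): Tmax is 5.5 and 6.8 h, and the 2 h sample is at 74% and 80%.
- The 2 h sample reaches 95% of Cmax only when ka is about 0.75 per h.
- A Tmax of 2 h needs ka of about 1.4 per h, seven times the stated value. With the other inputs unchanged, the 1000 mg single-dose Cmax would then be about 1,650 ng/mL, against 1,040 in Table 3.

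Within this model, then, the 2 h label and the Table 3 Cmax values cannot both hold.

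**Margin:** the QTc NOEL in Section 2.2.4 is 2,770 ng/mL. At 160 mg, the highest tabulated dose within the current Part 2 AUC limit, 2,770 / 210 = 13.2.

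**The case against.** No passage states a Tmax of 6.3 h; it is derived, and footnote a names no compartment model. Section 4.2.5 mentions a PBPK model whose output is not shown, so 2 h may have a source the reader cannot see. This stands. It is why the point claims a conflict and not that 2 h is the error.

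A reader might infer that QT monitoring in Part 2 misses the peak, or that a QTcF withdrawal would go undetected. The documents do not support that:

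- Days 7 and 14 have triplicates close to the modelled peak.
- Section 4.2.3 caps anticipated Part 2 steady-state exposure at the highest single-dose exposure found acceptable in Part 1. There, SoA Table A has repeated triplicate ECGs and telemetry.
- SAP Section 3.5.4 takes the maximum QTcF increase over the whole of Part 2, so the Day 4 and Day 10 readings are unlikely to determine it.
- On the legible schedule those days have only a predose PK sample, so they add no paired post-dose points to the concentration-QTcF plot.

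It is also fair to say that the plan can already re-time assessments. Section 8.5.1 lets timing changes be documented and approved without an amendment. But nothing triggers the change for Part 2, so the fixed 2 h stands by default, whereas Part 3 must follow observed Tmax.

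Finally, setting the time cohort by cohort would cause a problem of its own. Section 4.2.3 pools placebo across cohorts, and SAP Section 6.6.4 summarises dose-minus-placebo QTcF by timepoint. Cohort-specific times would mix nominal times in the pooled placebo data. This objection is right, and the fix below uses one common time.

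**Conclusion.** The inconsistency is real and minor. On the protocol's stated parameters, Tmax on Days 4 and 10 is about 6.3 h and the 2 h ECG sits at about 76% of that day's Cmax. This rests on the one-compartment assumption, supported by its reproduction of the protocol's exposure tables, and it is stable over the ranges of ka (0.1 to 0.3 per h) and half-life (5 to 12 h) tried.

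The documents do not settle which figure is wrong, so the conclusion is not that the ECG belongs at 6.3 h. Part 1 data should decide. The safety consequence is small for the reasons above. The 13-fold margin applies at 160 mg; higher doses need an amendment and would have less (at 300 mg, 2,770 / 390 = 7.1).

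**What to change.** Before Cohort 3 is dosed, replace the 2 h in footnote d with one time for all Part 2 cohorts: the Table C ECG timepoint (for example 2, 4 or 8 h) closest to the median Tmax observed in the Part 1 dose levels reviewed by then. State how a tie is resolved. If no amendment is planned, record the change under Section 8.5.1.

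The summary needed is already planned, since SAP Table 7 reports Tmax as "N, median, min, max". Staying on the Table C grid keeps Days 4 and 10 comparable with Days 1, 7 and 14 and keeps pooled placebo at one nominal time. A single time cannot follow every dose if Tmax shifts; Section 2.2.3 warns of "non-linear plasma PK and high variability in exposure at lower doses". That loss is acceptable: on the projection, 4 h and 8 h both lie within about 6% of the Day 4 Cmax.

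If the projection is right, the Part 1 sampling grid would show Tmax at 8 h (1,043 ng/mL, against 982 at 5 h and 918 at 12 h, at 1000 mg). The ECG would move to 8 h, at 98% of Day 4 Cmax. If observed Tmax is about 2 h, nothing changes. The cost is one footnote, no added procedures and possibly a small scheduling adjustment.

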14. History of sensitivity to heparin or heparin-induced thrombocytopenia *only if* heparin is used to flush IV catheters used during serial blood collections.
15. Unwilling or unable to comply with the lifestyle considerations outlined in [Section 5.3](#).
16. *In Part 2 only*, participants meeting criteria for contraindication to undergoing imaging assessments including –
 - Active placement of medical devices in/on thoracic cavity as these interfere with use of ultrasound-based imaging modalities, and MRI;
 - History/evidence of any of the following:
 - Contraindication to MRI such as ferric implant;
 - History of severe claustrophobia impacting ability to perform MRI during the study even despite mild sedation/treatment with a *short-acting* anxiolytic;
 - Inability to lie still within the *closed* environment of the MRI scanner *or* maintain a breath hold for the required period to acquire images *even despite* mild sedation/treatment with an anxiolytic.
17. Investigator site staff or Pfizer employees directly involved in the conduct of the study, site staff otherwise supervised by the investigator, and their respective family members.

Randomization Criteria – Parts 1, 2, and 3

Participants will be randomized into the study provided they have satisfied **all** the following criteria:

- Eligibility criteria outlined in [Section 5.1](#) and [Section 5.2](#);
- *In addition*, prior to dosing on Day 1, the results of the clinical laboratory tests (including urine drug test) **conducted upon each inpatient admission** must be deemed to have no clinically significant findings, in the opinion of the PI, and as such permit (continued) participation in this study.

In Part 1, participants in the 2 cohorts will be randomized per the scheme summarized in Table 5 with the actual dose administered following the proposed dose-escalation approach outlined in [Section 4.3.3](#) and [Table 3](#).

Table 5. Study C4171001 - Part 1 - Randomization Scheme

Cohort	Sequence	Period ^a			
		1	2	3	4 ^b
1 (n=8)	1 (n=2)	Placebo	Dose 3	Dose 5	Dose 7 ^c
	2 (n=2)	Dose 1	Placebo	Dose 5	Dose 7 ^c
	3 (n=2)	Dose 1	Dose 3	Placebo	Dose 7 ^c
	4 (n=2)	Dose 1	Dose 3	Dose 5	Placebo ^c
2 (n=8)	5 (n=2)	Placebo	Dose 4	Dose 6	Dose 8 ^c
	6 (n=2)	Dose 2	Placebo	Dose 6	Dose 8 ^c
	7 (n=2)	Dose 2	Dose 4	Placebo	Dose 8 ^c
	8 (n=2)	Dose 2	Dose 4	Dose 6	Placebo ^c

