8.2.4. Clinical Safety Laboratory Assessments

See [Section 10.2](#) for the list of clinical safety laboratory tests to be performed and the [SoA-Table A](#), [SoA-Table B](#), [SoA-Table C](#), and [SoA-Table D](#) for the timing and frequency. All protocol-required laboratory assessments, as defined in [Section 10.2](#), must be conducted in accordance with the laboratory manual and the [SoA-Table A](#), [SoA-Table B](#), [SoA-Table C](#), and [SoA-Table D](#). Unscheduled clinical laboratory measurements may be obtained at any time during the study to assess any perceived safety issues.

The investigator must review the laboratory report, document this review, and record any clinically relevant changes occurring during the study in the AE section of the CRF. Clinically significant abnormal laboratory findings are those which are not associated with the underlying disease, unless judged by the investigator to be more severe than expected for the participant's condition.

All laboratory tests with values considered clinically significantly abnormal during participation in the study or within **14 days** after the last dose of study intervention should be repeated until the values return to normal or baseline or are no longer considered clinically significant by the investigator or medical monitor.

If such values do not return to normal/baseline within a period of time judged reasonable by the investigator, the etiology should be identified and the sponsor notified.

Refer to [Section 10.6](#) for suggested actions and follow-up assessments in the event of potential drug-induced liver injury.

Participants may undergo **random urine drug testing** at the discretion of the investigator. Drug testing conducted prior to dosing must be negative for participants to receive study intervention.

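### Part 3 urine drug test: SoA Table D schedules it at the Period 1 admission only, while Section 5.2 requires an acceptable result from each inpatient admission before dosing

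*Protocol*

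**What the plan says.** **Part 3 schedule (Protocol 1.3, SoA Table D).** After Screening, the urine drug test appears once, on Day -1, with superscripts b and h. Footnote b begins "Procedures to be completed upon admission in Period 1" and adds Period 2 discharge for rows marked there; the drug-test row has no discharge mark. Footnote h reads "Results must be reviewed, by investigator, prior to dosing on Day 1" and does not mention Periods. On the same Day -1, the clinical laboratory tests, the serum pregnancy test and the urinalysis carry h alone.

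**Condition for dosing (Protocol 5.2, Randomization Criteria for Parts 1, 2 and 3).** Before Day 1 dosing, "the results of the clinical laboratory tests (including urine drug test) conducted upon each inpatient admission must be deemed" free of clinically significant findings in the investigator's opinion. The sentence ties this to participation, with the word continued in parentheses.

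**Part 1 schedule (SoA Table A).** The Day -1 drug test carries only footnote h, "Results must be reviewed prior to dosing on Day 1 in" each Period.

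**Section 8.2.4.** Random urine drug testing is allowed at the investigator's discretion, and "Drug testing conducted prior to dosing must be negative for participants to receive study intervention".

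**The concern.** Among the Day -1 laboratory rows of Table D, only the drug test is confined to Period 1. Section 5.2 names that same test as part of what must be acceptable at every admission, and the reference to continued participation shows that the rule is meant to reach admissions after randomization. If Part 3 has two admissions, staff who work from the schedule will give the second dose without a result that the eligibility text requires.

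What is at stake is a pre-dose check and clean conduct. Section 8 of the protocol treats adherence to the schedules as required and allows no waivers, so a mismatch between a schedule and an eligibility condition puts the site in an awkward position whichever text it follows.

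**Working it through.** The documents state no figure to reproduce here. The check compares the passages and counts tests against doses.

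**1. Inputs**
- Part 3 participants: 8 to 12 (Protocol 4.2.4, 9.2).
- Doses per participant: 2, one fed and one fasted, in random order (4.2.4).
- Spacing of doses: at least 5 days (Table D header).
- Inpatient row: Day -1 to 72 h, under a header covering Periods 1 and 2 (Table D).
- Drug tests scheduled after Screening: 1 under Table D; 1 per admission under Section 5.2.

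**2. Side by side**

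| Source | Applies to | Drug test before dose 1 | Drug test before dose 2 |
|---|---|---|---|
| Table D, footnotes b and h | Part 3 | Yes | Not scheduled |
| Section 5.2 | Parts 1, 2 and 3 | Yes | Yes, if there is a second admission |
| Table A, footnote h | Part 1 | Yes | Yes, in every Period |

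**3. Is there a second admission?** At the minimum spacing, dose 1 is on Day 1 and the 72 h point is on Day 4. Dose 2 is no earlier than Day 1 + 5 = Day 6, so the Day -1 of Period 2 falls on Day 5. Table D thus shows a stay ending on Day 4 and another starting on Day 5 or later. That suggests discharge and return but does not state it, and Figure 3 is not reproduced in the text available.

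**4. Count, if there are two admissions**
- Total dosings: 8 × 2 = 16 to 12 × 2 = 24.
- Dosings with no scheduled admission drug test: 8 × 1 = 8 to 12 × 1 = 12.
- Share: 8/16 = 12/24 = 50%.

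**5. Count, if there is one continuous stay.** There is one admission and one test, Section 5.2 is met, and no dosing is affected.

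**The case against.** **One continuous stay.** This is the strongest counter-argument. Footnote b pairs admission in Period 1 with discharge in Period 2, which would fit a single stay. The Day -1 reviews of alcohol and tobacco use and of concomitant treatments also carry b in Table D but have no such limit in Table A; dropping them makes more sense if participants never leave. At the 5-day minimum, staying in would be practical. This reading stays open, and the conclusion is conditional because of it. But no visible passage states it. The phrases admission in Period 1 and discharge in Period 2 read just as naturally as one admission and one discharge among several, and Table D ends the stay at 72 h. Table 12 footnote b speaks of each admission in all three Parts, but that wording also covers Part 2, which has one stay, so it does not settle the point.

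**Section 5.2 only governs review of tests scheduled elsewhere.** Exclusion criterion 8 asks for the drug test at Screen, and again on Day -2 in Part 2 only, with no per-Period test for Part 3. That has some force. Still, Section 5.2 names the drug test explicitly and refers to each admission and to continued participation, so a reader would expect one result per admission.

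**Discretionary testing under Section 8.2.4.** A site could close the gap this way, so the check is not impossible. But an option does not secure a mandatory condition, and the rule that a pre-dose test must be negative does not schedule one.

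**A stronger reading that the documents do not support.** A reader might infer that undetected drug use between Periods would bias the food-effect ratio. The minimum panel in Table 12 is cocaine, opiates/opioids, benzodiazepines and amphetamines, and nothing in the documents says that any of these alters PF-07202954 exposure. Section 2.2.2 reports a low risk of interaction with CYP3A4 inhibitors or inducers and names potent OAT3 inhibitors as the concern. The contrast is fed versus fasted in randomized order, not Period 1 versus Period 2, and the SAP model for Part 3 (Section 5.2) includes sequence and period. No shift in the ratio can be claimed.

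**Conclusion.** The inconsistency is in the current text: Table D limits the Part 3 admission drug test to Period 1, Section 5.2 asks for it at each admission, and Table A shows Section 5.2's rule carried out in Part 1. If Part 3 participants are readmitted for Period 2, the second dose of every participant, 8 to 12 of 16 to 24 dosings, has no scheduled drug-test result, and keeping to Table D means not meeting Section 5.2. This rests on readmission, which is an inference from the inpatient row. Under one continuous stay the conflict disappears and only the wording needs clarifying.

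The matter is minor. It concerns a pre-dose check in an optional Part of the study. It changes no sample size, model or confidence interval, and no bias in the primary comparison has been shown.

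**What to change.** Reconcile Table D and Section 5.2 before Part 3 starts. The choice is the sponsor's.

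- **If there are two admissions and Section 5.2 is meant to hold:** remove superscript b from the Day -1 urine drug test in Table D, so that the test is done and reviewed at both admissions. Naming each Period in Table D's footnote h, as Table A does, would remove any doubt. Cost: 8 to 12 extra spot tests, on urine already collected for the Day -1 urinalysis, plus the edit.
- **If one continuous stay or a Period 1-only test is intended:** say so in Table D and state the Part 3 position in Section 5.2. Cost: wording only.
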